## 8. Retention Strategy for Participants

Mott Children's Health Center serves children and families 200% of the poverty level and below. While the children are receiving care at Mott Children's Health Center and the University of Michigan School of Dentistry, their parents, however, are not. The intention of this study is to assess the effect of SDF, yet we are very interested to promote oral health (which in the case of young children is very dependent on family health), so we will seek a study participant fee to

account for transportation costs to study visits and funds that can be used for assistance with the oral health care needs of any family members of the study participants, if necessary. Parents will receive \$50 for their child's participation in the intervention appointment. Following successful recall contacts, the parents will be provided with a \$10 reimbursement (this has been used very successfully by members of the study team in an NIH study to increase retention over time). Parents will receive payment for each of three clinical recall visits: \$60 at 3 months, \$70 at 6 months and \$80 at 12 months. Following initial intervention (\$50), four recall contacts (\$10 each) and three recall visits (\$210 total) this will result in a total possible participation fee of \$300. All payments will be provided in the form of a gift card, and given to the parent of a participant. The parent will acknowledge receipt. Payments are funded by Delta Dental, study sponsor, and are in no way funded by Mott Children's Health Center or the University of Michigan School of Dentistry.

## **9. Withdrawal Procedures**

Subjects will have the right to withdraw at any time. Alternative conventional treatment can also be provided to the SDF group at any time, if it is believed by the provider to be in the patient's best interest. Reasoning will be recorded, as a preference for or against one treatment arm may provide further information as to public acceptance of a treatment, and these subjects will be withdrawn, *CRF 04 Treatment Deviation* (Appendix 10, CRF 04) and appropriate additional forms will be completed and the parent will receive a *Study Completion or Disenrollment Letter* (Appendix 11). Although no adverse events are expected *CRF 15 Unanticipated Problem & CRF 16 Adverse Event Logs* will be available if necessary (Appendix 10, CRF 15 & 16). In the event that the protocol is ever deviated from (ie. Missed recall or appropriate study procedure not completed) a *CRF 14 Protocol Deviation* (Appendix 10, CRF 14) will be completed.

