### **4.2. General Outline**

Children, 2-10 years of age will be invited to participate. The original study site is Mott Children's Health Center (MCHC) in Genesee County, Michigan. Following a slow recruitment period, the University of Michigan School of Dentistry (UMSOD) Children's Clinic was added as a second study site. Given the current data in the literature, the combined failure rate for conventional restorative techniques (e.g. compomers) is approximately 29% at one year follow-up, while application of silver diamine fluoride has a failure rate of 63% at one year follow-up, with increased success over time. Although the failure rate of SDF at one-year follow-up seems alarming, as indicated by Zhi, *et al.* it may be possible to increase the success rate with additional applications providing success rates up to 90.1% at 24 months. Using these data,  $\alpha$ -value of 0.05 and a Power set at 80%, the resulting sample size would be 68 (34 per group) as calculated using the software, nQuery (Appendix 1). To account for 30% attrition, the final number needed for the initial study will be 98 (92 for 25% attrition, 86 for 20% attrition). Subjects will be contacted by phone regularly and invited to two intermediate clinic visits (plus a final study visit) to reduce attrition (Table 1). Given a review of the current literature of the few Randomized Controlled Clinical Trials involving SDF worldwide, the majority of this research has been completed with pre-school aged children. Almost all research discusses arresting or prevention of caries in the

primary dentition, as well as prevention of caries on first permanent molars. Due to the strength of the current research, this study will be focused on the primary dentition of children in the U.S. These children and their parents will be approached when presenting for examination/recall/or treatment at Mott Children's Health Center, Flint, MI, or the University of Michigan School of Dentistry Children's Clinic, Ann Arbor, MI. Interested families with children that qualify following screening examination will be provided with an *Informed Consent/Assent* (Appendix 3) and an *Enrollment Information Form* (Appendix 4).

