## 6. Study Visits and Intermediate Contacts

Recalls for both groups will occur via phone questionnaire as well as follow-up visits. Participants will be contacted at 1 month, 2 months, 4.5 months and 9 months ( $\pm$  2 weeks) following restoration placement or application of SDF. Subjects will need to present to the clinic for follow-up visits at 3 months ( $\pm$  6 weeks), 6 months ( $\pm$  6 weeks), and for study completion at 12 months ( $\pm$  6 weeks) (Table 1). Subjects will also be called to schedule and confirm these follow-up visits; these short calls will require no payment to the study subjects. In the case of an emergency, an emergency visit will be scheduled at Mott Children's Health Center or the University of Michigan School of Dentistry. An emergency will be evaluated and treated according to the AAPD guidelines, followed by completion of appropriate case report forms (CRFs) and reporting to IRBs and study sponsors (Appendix 10, CRF 14-17). In the event of minor or major failure in either study group, the subject will be withdrawn from the study and teeth will be given the appropriate treatment as stated in the AAPD Guidelines free of charge, these teeth will be categorized as a failure, and a *CRF 04 Treatment Deviation CRF (Appendix 10, CRF 04)* will be completed.

**Table 1.** Patient Contact Interval

Patient Contact	Recall Interaction	Time Scale
Clinic Visit #1	Consent/Accent, baseline questionnaires, initial caries assessment, radiographs*, intervention	T = 0
Intermediate Contact	Attrition prevention, update contact information, follow-up on pain	T = 1 month, 2 months (Additional reminder for Clinical Visit #2)
Clinic Visit #2	Assessment for major and minor failure & assessment of pain and parent satisfaction	T = 3 months
Intermediate Contact	Attrition prevention, update contact information, follow-up on pain	T = 4.5 months (Additional call reminder for Clinical Visit #3)
Clinic Visit #3	Reapplication of SDF in that group; Assessment for major & minor failure, radiographs*, and assessment of pain and parent satisfaction	T = 6 months

Intermediate Contact	Attrition prevention, update contact information, follow-up on pain	T = 9 months (Additional call for scheduling/reminder for Clinical Visit #4)
Clinic Visit #4	Assessment for major & minor failure, radiographs*, and final questionnaires	T = 12 months

\* Radiographs will be obtained only if an existing radiograph within 30 days of the visit is not available.

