## **11. Potential Limitations**

An initial potential problem in the study may be to obtain the 98 patients needed per the power analysis calculation. Hopefully this will not remain too much of an obstacle, as children are frequently seen at Mott Children's Health Center and University of Michigan School of Dentistry Children's Clinic with carious lesions of this nature. When enrolling in this study, parents are either simply enrolling their children in a study where they would be provided the care that they would otherwise be provided outside of the study or, if receiving the alternative SDF treatment, they always have the ability to opt out and receive their definitive, conventional treatment. At the completion of the study, children who received care in the SDF group will have their study teeth restored according to AAPD guidelines or monitored for exfoliation, whichever is deemed most appropriate by their final provider or elected by the parent.

In order to prevent confusion and withdrawal from the study following intervention due to misinformation, all residents at Mott Children's Health Center and the University of Michigan School of Dentistry Children's Clinic who are providers for this study will be standardized in terms of the presentation of the study to the parents and patients and in the informed consent and assent process for the parents and children involved. It is important that these patients and their parents understand especially how the tooth may look following treatment. Teeth treated with SDF may become darker, and it is important to standardize this presentation by all residents so that patients are not withdrawing from the study simply because they were unaware of these anticipated consequences of the treatment.

In order to achieve a sample population of this size in such a short amount of time, five or six residents at each clinical site will be completing the screening, treatment, and recall of these patients. While having many providers is a limitation of the study, all providers will be trained and calibrated in their assessment of the tooth color and hardness as well as in their SDF application technique.

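### SDF children switched to conventional treatment before any failure criterion is met have no defined outcome and no place in the analysis, which can bias the comparison in either direction

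*Combined protocol and SAP*

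**What the plan says.** All references are to the combined protocol and SAP.

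- **Section 9 (Withdrawal Procedures):** "Alternative conventional treatment can also be provided to the SDF group at any time", if the provider thinks this serves the child. The reason is recorded, "these subjects will be withdrawn", CRF 04 is completed, and the parent receives a completion or disenrollment letter. No failure criterion has to be met.
- **Section 11 (Potential Limitations):** of parents whose child receives SDF, "they always have the ability to opt out and receive their definitive, conventional treatment".
- **Section 6 (Study Visits):** children with minor or major failure, in either arm, are also withdrawn, but "these teeth will be categorized as a failure". CRF 04 is used here too.
- **Section 4.4 (Allocation and Blinding):** parents, children and dentists cannot be blinded. If treatment is failing in either arm, the provider may withdraw the child, and families in either arm may withdraw for any reason. Reasons are recorded.
- **Section 10 (Statistical Analysis):** the primary outcome is the proportion with major failure over 12 months, analysed by a binomial mixed model. Dropout rates are compared by chi-square test. No analysis population, handling of withdrawn children or sensitivity analysis is given.

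**The concern.** The switch to the comparator treatment before failure is written for the SDF arm only. Once an SDF tooth has been restored and the child disenrolled, the 12-month result of the assigned strategy is not observed. The people who decide on the switch know the assignment, and section 11 has the same residents doing screening, treatment and recall.

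The two arms also differ in what re-treatment implies. Under Table 2, secondary caries, a lost restoration, or fracture or wear needing repair is already a minor failure in the conventional arm, so re-treatment there will usually be counted. Restoring an SDF tooth on judgement alone is not in itself a failure.

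At stake is the failure comparison itself. If children leave because the tooth looks poor, the remaining SDF children are a better-than-average subset. If they leave for other reasons, the effect may be nil or reversed. Because the plan does not say how these children are handled, the choice could be made after results by arm are known.

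**Working it through.** **Step 1. Routes out of follow-up, side by side**

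| Route | Arm | Table 2 criterion required? | Outcome assigned |
|---|---|---|---|
| Minor or major failure (section 6) | Both | Yes | Failure |
| Provider withdraws because treatment is failing (section 4.4) | Both | Not stated | None stated |
| Family withdraws (sections 4.4, 9) | Both | No | None stated |
| Provider gives conventional treatment (section 9) | SDF only | No | None stated; child withdrawn |
| Parent opts out to conventional treatment (section 11) | SDF only | No | None stated |

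Only the first route has a defined outcome. The last two exist in one arm only.

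**Step 2. The plan's own figures**

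Inputs from section 4.2: the conventional failure rate "is approximately 29% at one year follow-up"; "application of silver diamine fluoride has a failure rate of 63% at one year follow-up"; alpha 0.05; power 80%. The standard two-sided formula for two proportions, with pooled variance and no continuity correction, gives

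n = [1.960 × √(2 × 0.46 × 0.54) + 0.842 × √(0.29 × 0.71 + 0.63 × 0.37)]² / 0.34² = 32.5, so 33 per arm or 66 in total.

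This is within 2 of the stated 68. Power at 34 per arm is 81.8%. For attrition, 34 / 0.7 = 48.6, so 49 per arm: "To account for 30% attrition, the final number needed for the initial study will be 98" reproduces. The sample size arithmetic is not in question.

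**Step 3. Illustration on the combined failure rate**

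Let k be the SDF children switched and lost, f the share of them who would have failed, and F the failures in the full SDF arm. Then

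observed SDF rate = (F − k × f) / (49 − k).

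The documents give neither k nor f; both are assumptions. The upper value, k = 15, is about 30% of 49. At the planning rate, 49 × 0.63 = 30.9, so F = 31 (63.3%).

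| k | f = 1 (all would fail) | f = 0.63 (typical of the arm) | f = 0 (none would fail) |
|---|---|---|---|
| 5 | 26/44 = 59.1% | 63.3% | 31/44 = 70.5% |
| 10 | 21/39 = 53.8% | 63.3% | 31/39 = 79.5% |
| 15 | 16/34 = 47.1% | 63.4% | 31/34 = 91.2% |

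Against 29% in a conventional arm with no losses, the f = 1 column takes the odds ratio from 4.2 (k = 0) to 3.5, 2.9 and 2.2, and power from 94% to 84%, 66% and 39%. In the f = 0.63 column power is still 92%, 91% and 89%.

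Section 3.5 reports 53% arrest at 12 months with biannual application, that is 47% failure, which is closer to this trial's 6-month reapplication. With F = 49 × 0.47 = 23.03 and k = 10:

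- f = 0.9: (23.03 − 9) / 39 = 36.0%
- f = 0.47: (23.03 − 4.7) / 39 = 47.0%
- f = 0.2: (23.03 − 2) / 39 = 53.9%

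With f = 0.9, k = 5 gives 42.1% and k = 15 gives 28.0%. So f sets the direction of the bias, while k mainly sets its size.

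**Step 4. Counting every switch as a failure**

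If switched children are typical of the arm (f = 0.63), counting all of them as failures gives (31 − k × 0.63 + k) / 49 = 67%, 71% and 75% for k = 5, 10 and 15. That overstates the true 63.3%. It is therefore a bound, not a correction.

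**The case against.** The strongest reply is that this is an ordinary missing-data gap and that several stronger readings go beyond the text. Much of that stands.

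- **That switched children are counted as non-failures.** A reader might infer this from the contrast between sections 6 and 9. No sentence says so, both sections use CRF 04, and the content of that form cannot be checked here. Their status is undefined.
- **That only the SDF arm loses children.** Section 4.4 lets providers withdraw failing children, and families withdraw, in either arm. Only the switch to conventional care is specific to SDF.
- **That the loss must flatter SDF.** Section 9 records reasons because preference and public acceptance are of interest, and section 11 discusses withdrawal over darkened teeth. Such exits may be unrelated to failure.
- **That the judgement goes unrecorded.** Section 9 requires the reason to be recorded. The gap is that section 10 never uses it.
- **That the 30% is an allowance for this loss.** It is a general planning figure for total attrition.
- **That many worrying teeth escape counting.** Soft dentin or a larger lesion is already a minor SDF failure, so many would be counted under section 6. The gap is confined to switches before any criterion is met. This protects the combined rate better than the primary outcome, since a minor failure is not a major one.

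The chi-square test on dropout could reveal an imbalance but not correct it. A mixed model can use visits before the switch, but it adjusts only for what the model contains. A provider's concern before any criterion is met is not in the binary outcome.

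**Conclusion.** The point holds as an undefined-outcome problem with a possible bias, not as a demonstrated bias for SDF. Sections 9 and 11 create a pre-failure switch in one arm, section 9 withdraws those whom the provider switches, no section gives them an outcome, and section 10 neither analyses children as randomised nor says how withdrawals are handled. Decisions are unblinded.

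The direction depends on why children switch. It favours SDF if switches reflect clinical concern, and is neutral or unfavourable to SDF if they reflect appearance or preference. With 5 to 15 of 49 SDF children lost and a full-arm combined failure rate of 63.3%, the observed rate could lie anywhere from 47.1% to 91.2% at the extremes, and does not move if leavers are typical of the arm. These scenarios rest on assumed leaver numbers and prognosis and on no loss in the conventional arm. They concern combined failure. The primary outcome is major failure, for which the documents give no expected rate, so the effect on the primary result cannot be computed.

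**What to change.** No change to the clinical rules is proposed; the changes concern follow-up, outcome definition and analysis.

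1. Reconcile sections 4.4, 6, 9 and 11 on the outcome status of children switched or withdrawn before a failure criterion is met.
2. State in section 10 that all randomised children are analysed in their assigned arm.
3. In section 9, separate ending study treatment from leaving the study: keep the scheduled 12-month visit and outcome where consent allows. Say how an SDF tooth that has since been restored is scored, including which column of Table 2 applies.
4. Pre-specify sensitivity analyses, applied the same way in both arms. One should use the recorded CRF 04 reasons to count switches or withdrawals for clinical concern as failures. Add best- and worst-case bounds for children with no 12-month outcome.

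The cost is some wording, a little more follow-up and a little more analysis. Section 8 already provides for the 12-month payment, and section 11 already keeps children who miss an intermediate visit until the final one. The SDF result may look less favourable.

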### **3.4. Negative Aspects of Silver Diamine Fluoride**

In addition to the numerous apparent positive effects of SDF there are a minimal number of drawbacks, the most notable being the black stain it leaves on the carious dentin. While esthetically unpleasing to some, this black stain is not of any physical harm to the patient. In fact when compared to applications of sodium fluoride and no treatment, all treatments had teeth presenting at recall with blackened dentin. Recent studies have shown this black discoloration appears to be a non-issue, as the coloration of the teeth following treatment did not decrease patient satisfaction. However, additional research has still been aimed at reducing the black discoloration of the tooth by placing potassium iodide (KI) following SDF application or by completely placing an alternative agent, such as ammonium hexofluorosilicate ( $(\text{NH}_4)_2\text{SiF}_6$ ). Placing potassium iodide may eliminate the staining, but whether this reduces the effectiveness of the SDF is still in need of further evaluation, especially *in vivo*. Research on ammonium hexofluorosilicate, on the other hand, shows that it is not effective in reducing caries progression and is therefore not a viable replacement option to SDF.

The most common concern with any product used intraorally is its compatibility with intraoral soft-tissues. Recent research has confirmed that tissue ulcerations and argyria were not present following treatment with SDF. Only transient mild erythema of the gingiva near the SDF-treated tooth and a metallic taste in the patients' mouths were noted in some patients, supporting that the use of silver diamine fluoride is quite safe.

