### **5.2. SDF management of caries**

- The selected tooth with notable decay into dentin will be isolated with cotton rolls.
- No caries removal will be performed, except for food or other obvious debris.
- Tooth will be dried with gauze and SDF solution will be placed on the carious dentin until it is saturated.
- Excess SDF will be blotted dry with a cotton pellet.
- A second application of SDF solution will then be placed to ensure that the entire carious surface is wetted, and excess will again be blotted with a cotton pellet.
- Following the second application of SDF, the area will be isolated for 3 minutes to allow for ample drying before allowing contact with saliva and soft tissues
- Should the SDF come in contact with any soft tissues, soft tissue should immediately be wiped with a saline wipe
- Following completion of the SDF intervention visit, the provider will complete the CRF 03 *Intervention Visit: Silver Diamine Fluoride* CRF (Appendix 10, CRF 03).
- A second application of SDF will be applied at 6 month recall, following the same protocol as noted above (Due to the potential for increased caries arrest rate with a 6 month application).
- Any new carious lesions that develop after the initial treatment will be recorded, and treated using conventional treatment methods and will not be included in the study.
- Following the completion of this study, teeth in the SDF group will be treated according to AAPD guidelines or observed for exfoliation. The parent of an SDF treated child can elect a restoration following AAPD guidelines at the 12 month visit.

Both groups will receive the following, according the standard procedures at the MCHC/UMSOD:

- Oral Health Instruction (OHI) and diet instruction
- Tooth brushing/dentifrice use at home
- Fissure sealants for permanent teeth will be placed if deemed necessary.
- Traditional preventative care at recalls based on AAPD guidelines (Regular recall exams, prophylaxis, scaling, flossing, and fluoride varnish at 6 month recalls will be provided for both treatment arms. Special care will be taken to not apply fluoride varnish directly to the carious lesion which is being treated with SDF.)

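### Section 9 expects no adverse events although Section 3.4 reports gingival erythema and metallic taste after SDF, and no described step asks about them, so they may be under-captured or inconsistently classified

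*Combined protocol and SAP*

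**What the plan says.** Section 9 (Withdrawal Procedures) is where the protocol states its expectation for harms: "Although no adverse events are expected". It then says that "CRF 15 Unanticipated Problem & CRF 16 Adverse Event Logs" can be used if the need arises.

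Section 3.4 summarises earlier SDF studies. It states that "tissue ulcerations and argyria were not present following treatment with SDF", and then gives what was seen in some patients: "Only transient mild erythema of the gingiva near the SDF-treated tooth and a metallic taste".

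Section 5.2 has a precaution that begins "Should the SDF come in contact with any soft tissues" and continues with a wiping step. It states no step for recording such contact. The same section has the provider complete CRF 03 after the SDF visit, and schedules a second application at the 6-month recall.

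Table 1 in Section 6 gives the content of every intermediate contact as "Attrition prevention, update contact information, follow-up on pain". For the 3-month clinic visit it gives "Assessment for major and minor failure & assessment of pain and parent satisfaction". The 6-month visit adds reapplication and radiographs. The 12-month visit covers failure, radiographs and the final questionnaires. Section 7.1 adds parent and child questionnaires at the recall visits. Section 6 sends emergency visits to CRFs 14 to 17, with reports to the IRBs and sponsors.

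Sections 7 and 10 name no adverse-event outcome and no adverse-event analysis.

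**The concern.** A protocol that describes two local effects of its test product cannot, read literally, also expect none. The sentence in Section 9 matters because it is the only reference that providers have for deciding whether an event is expected. Section 11 plans five or six residents at each of two sites, so 10 to 12 people will make that decision. The training and calibration described in Sections 10 and 11 cover ICDAS, tooth color, hardness, lesion size, SDF technique and the presentation of the study to families. Adverse events are not mentioned. With no list of expected effects, one resident might ignore redness at the gum, another might enter it on CRF 16, and a third might file it as an unanticipated problem on CRF 15.

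Collection is the second issue. If nobody asks about a mild, short-lived effect, its count depends on who volunteers it. Section 4.4 says that families and dentists cannot be blinded, so volunteering may differ between arms. A low count of local reactions to SDF could then reflect how they were collected. Parent and patient acceptability is an objective in Section 2, and an unpleasant taste bears on it.

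**Working it through.** The plan gives no figure to reproduce. The check compares sections, works through the schedule, and illustrates size under assumed rates.

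**1. Expectation against background.** Section 9 expects no adverse events. Section 3.4 reports erythema and metallic taste in some SDF patients. These conflict. Section 5.2 adds little: its soft-tissue sentence is a conditional precaution and predicts no event.

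**2. What is asked, and where.**

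| Occasion | Content stated in the text | Gum or taste item stated? |
|---|---|---|
| Treatment visit | CRF 02 or 03 completed by the provider | No; items not in the published text |
| Contacts at 1, 2, 4.5 and 9 months | Retention, contact details, pain | No |
| 3- and 6-month visits | Failure, pain, parent satisfaction, questionnaires | No; questionnaire items not in the published text |
| 12-month visit | Failure, final questionnaires | No; same limit |
| Emergency visit | CRFs 14 to 17, questionnaires | No; same limit |

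The failure criteria in Table 2 concern the lesion, restoration and pulp. None concerns soft tissue or taste.

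**3. Time from application to the next scheduled contact.** The inputs are the Section 6 windows: ± 2 weeks for the contacts (read as applying to all four) and ± 6 weeks for the clinic visits. One month is taken as 52/12 = 4.3 weeks.

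- First application at month 0, next contact at 1 month: 4.3 − 2 = 2.3 weeks to 4.3 + 2 = 6.3 weeks, or about 2 to 6 weeks.
- Reapplication at the 6-month visit, next contact at study month 9: nominally 9 − 6 = 3 months = 13 weeks. At the extremes of both windows this is 13 − 6 − 2 = 5 weeks to 13 + 6 + 2 = 21 weeks.

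Section 3.4 calls the erythema transient but gives no duration. A transient effect could well have resolved before either contact.

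**4. Illustrative size.** With 98 children allocated 1:1, the SDF arm has 98/2 = 49. The documents give no incidence, so p is assumed. Expected cases after the first application are 49p, and the chance of at least one is 1 − (1 − p)^49.

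| Assumed p | Expected cases | Chance of at least one |
|---|---|---|
| 2% | 0.98 | 63% |
| 5% | 2.45 | 92% |
| 10% | 4.9 | 99% |

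Across this range the trial would more likely than not see at least one such effect, which fits poorly with an expectation of none. The table says nothing about how many would be recorded.

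**The case against.** The strongest reply is that the forms themselves cannot be seen. Appendix 10 holds the CRFs, and their items are not in the published text. Table 1 only summarises each contact. CRF 03 is completed on the day of application, when soft-tissue contact or a complaint about taste would be observable. The 6-month reapplication also takes place at a clinic visit with its own forms. A question on gums or taste may already exist. This stands, and the conclusion is conditional on it.

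Three stronger readings are tempting, and the documents support none of them.

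- A reader might infer that known effects will be either missed or filed as unanticipated problems. CRF 16 is a separate adverse event log, and a known mild effect can be entered there as an ordinary adverse event. The risk is inconsistent classification.
- A reader might infer that all scheduled contacts ask only about pain. That fits the listed content of the intermediate contacts. The clinic visits also assess failure and use questionnaires, and those at 3 and 6 months also cover parent satisfaction.
- A reader might infer that no such effects would be captured. That requires every effect to resolve before the first contact and no form to ask, and neither is established.

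It can also be said that safety is not a stated objective and that Section 3.4 presents these effects as mild and as support for safety. That is fair, and it limits the importance of the point. It does not remove the conflict between Sections 3.4 and 9 or supply an analysis.

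**Conclusion.** The point holds and is of modest importance. The conflict between Sections 9 and 3.4 is plain from the text and does not depend on any unseen form. The absence of a planned adverse-event analysis is also plain from Section 10. The risk of under-capture is supported by the listed content and timing of the intermediate contacts. It rests on two assumptions: that the CRFs contain no item on gums or taste, and that the effects usually clear within a few weeks. Inconsistent classification between CRF 15 and CRF 16 is a risk because no list of expected events is given.

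The number of affected children cannot be derived from the documents. The range of about 1 to 5 cases among 49 comes entirely from assumed rates of 2% to 10%. The sample size, the primary outcome and the efficacy comparisons are not affected.

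**What to change.** 1. Reword the Section 9 sentence so that it names gingival erythema and metallic taste as expected local effects, consistent with Section 3.4.
2. Check the existing forms. Unless they already ask, add yes/no items for both effects, in both arms, to CRFs 02 and 03 at the end of the treatment visit, to CRF 07 at the intermediate contacts (including the first contact and the 9-month contact), and to the 6-month visit form.
3. Record these effects on CRF 16 as expected adverse events, and keep CRF 15 for events outside the list. Add this distinction to the residents' training.
4. Add a sentence to Section 10: tabulate the solicited effects by arm, with the number of children asked as the denominator.

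The cost is one reworded sentence, one added sentence, a few tick boxes and a short training item. No visit or staff are added. The small downside is that more minor events will be recorded.
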